6.2 Duration of Study and Visit Schedule

Following the pilot test, the study plans to recruit over a period of 10 months a total of 2,000 adults (ages 18 or older), who complete the study from all sites combined. Each participant will be seen only once for this study (no follow-up visits). Initial screening and all assessments will occur during the participant index visit. The total duration of individual participation in the study is expected to be from about 30 minutes to 1 hour (depending on how many substances they report having used).

Compensation:

To increase participants' retention to complete all assessments and to compensate participants for their time, each participant will be paid \$20 for completing the assessments and an additional \$10 for providing an oral fluid sample for drug testing.

7.0 STUDY POPULATION

7.1 Inclusion Criteria

- 1. Primary care patients ages 18 years or older at one of the participating CTN Node study sites.
- 2. Ability to provide informed consent.

7.2 Exclusion Criteria

- 1. Inability to comprehend spoken English.
- 2. Inability to self-administer the iPad tool due to physical limitations.
- 3. Previously enrolled in this study.

7.3 Subject Recruitment

For a target sample size of 2,000 adult completers, the New York Node site is expected to recruit approximately 40 participants per month (approximately 10 adults per week per site) in order to reach the recruitment target (400 completers) within 10 months. The site/s in Mid-Atlantic Node and Southern Consortium Node will be expected to recruit approximately 80 participants per month (approximately 20 per week) in order to reach the recruitment target (800 completers) within 10 months. However, the sites may continue to recruit competitively after they have reached their recruitment target until the entire study reaches 2,000 participants who have completed all of the assessments.

It is assumed that 50% of primary care adult patients who are approached to explore their willingness to participate in the study either decline or are ineligible for the study. The participants will be directly recruited from the clinic's waiting rooms, after obtaining IRB approval.

7.3.1 Special Populations to Consider

Given the demographic characteristics of the study sites, we will be able to recruit an adequate sample of women and nonwhite participants. Participants who are considered prisoners by OHRP guidelines will not be included in the study.

7.4 Study Sites

7.4.1 Number of CTN Node Study Sites

There will be three CTN Nodes with several study sites involved in the study:

- Mid-Atlantic Node.
- New York Node.
- Southern Consortium Node.

7.4.2 Study Site Characteristics

Study site characteristics were developed based on the need to obtain data from adult patients enrolled in primary care. Sites will be selected from among clinics with the following characteristics:

- 1. Primary care clinic.
- 2. Clinic serves a sufficient number of male and female patients that would be potentially eligible to participate in the study.
- 3. Clinic has adequate space to accommodate study staff and activities.

7.4.3 Rationale for Study Site Selection

The selection of study sites is based on the applicability of the expected finding to adults in the community, cost, and feasibility. For consideration of the generalizability of study results to community-based primary care patients, the study will be conducted in primary care settings.

8.0 OUTCOME MEASURES

8.1 Primary Measure of Interest (Screen, TAPS Tool)

Unlike an intervention trial that seeks to examine a specific outcome in relation to an intervention, the focus of this study is to identify a set of questions useful for detecting adults with use, sub-threshold SUD, and SUD of tobacco, alcohol, prescription medications, and illicit drugs. Thus, we plan to examine the sensitivity, specificity, and ROC for each item of a) the 4-item screen and b) the TAPS Tool, against items from this study's gold standard measures. As such, all items of the screen and TAPS will be examined.

8.2 Criterion Measures

The Full ASSIST, AUDIT-C, TLFB, modified CIDI-SAM-2, Fagerström, smokeless tobacco questionnaire, and Oral Fluid Testing will be the gold standards (criterion) in separate analyses for each corresponding substance (tobacco, alcohol, cannabis, etc.) as appropriate. We intend to examine each item in the TAPS Tool, against the corresponding item(s) on the gold standard measures. Thus, for example, the tobacco item on the TAPS Tool would be compared to the tobacco item on the ASSIST, while the marijuana item on the TAPS Tool would be compared to the marijuana item on the ASSIST. Furthermore, we want to compare the TAPS Tool scores by substance with the "gold standard measure" (Full ASSIST for all substances, Fagerström for tobacco, and modified CIDI-SAM-2 for all substances) to determine whether they met criteria for a sub-threshold SUD or SUD for that particular substance use disorder.

9.0 STUDY PROCEDURES FOR PILOT TESTING OF SCREEN AND TAPS TOOL

After the programming and testing of the electronic version of the TAPS Tool is completed (including a measurement of administration time for both the screening and brief assessment sections separately and in total), the investigators will conduct a pilot test with 30 participants across the study sites. Adult primary care patients will be recruited and asked to complete the interviewer-administered and self-administered (iPad) versions of the TAPS Tool and subsequently asked during an individual meeting with study staff to provide their feedback on the tool.

During the use of the iPad, the research assistant will observe the participant's use of the iPad, ask about any visible difficulty, and make text notes describing problems and remediation to address this difficulty.

After the participants complete the tool, they will be asked to complete a brief survey asking about the feasibility (e.g., time required to complete [in minutes]; user-friendliness [Likert scale 1 to 5]; need for assistance: [yes/no with comment box]), acceptability (e.g., comprehension of the items including smokeless tobacco item [yes/no with comments box], likelihood of responding accurately [Likert scale]), and preference for format (self-administration versus interviewer-administration [preference choice vs. no preference]) of the tool in primary care settings.

These survey items will be rated by participants on a 5-point Likert Scale to capture their view of their experience with the interview-administration vs. self-administration of the tool. The survey will be as follows:

How much do you agree with the following statements on a scale of 1-5 where:

1 = strongly disagree 2 = disagree 3 = neither agree nor disagree 4 = agree 5 = strongly agree

- **Q1.** These questions were easy to understand.
- **Q2.** I was comfortable answering these questions.
- **Q3.** I answered these questions as honestly as I could.
- Q4. I would be willing to answer questions like these at my doctor's office.
- **Q5.** I think my friends would answer these questions honestly at their doctor's office.
- **Q6.** The iPad touch screen was easy to use.
- **Q7.** I would prefer that a person asked me these questions in the doctor's office instead of answering them myself on the iPad.
- **Q8.** I would prefer answering these questions on an iPad instead of having a person ask me.
- **Q9.** The voice recording was helpful.

Q10. I would be comfortable sharing my answers about drug use with my doctor.

Each participant will be paid \$20 for their time and contribution to the study. Based on each participants' response, the screen and TAPS Tool will be refined to improve the wording and workflow accordingly.

10.0 STUDY PROCEDURES FOR PRIMARY STUDY OF THE TWO-STAGE TOOL

10.1 Recruitment and Informed Consent Procedures

Study recruitment procedures:

To avoid interrupting patient care, the logistics of conducting screening in a medical setting require that the screening process be relatively brief. During defined recruitment hours, research staff assigned to the study will screen primary care patients who are possibly eligible for the study. Depending on the patient flow, patients will be approached either prior to or after the evaluation by a clinician.

Research staff will approach patients consecutively in the clinic waiting area and ask them if they are willing to participate in anonymous screening for participation in a health study. Participants will provide verbal (not signed) consent for the anonymous collection of screening data, using a brief IRB-approved script. For each day of screening, the number of patient refusals and other reasons for patient inability to participate will be recorded on the Recruitment Form to determine whether they met inclusion criteria (and if not, why not: lack of spoken English comprehension; younger than 18 years old; unable to provide informed consent, physically unable to use the iPad, or other). The RA will document the screening and eligibility status of all individuals approached on the Recruitment Form. The research staff will screen patients according to the Operations Manual procedures and local manual of operations. Screening efforts will continue until recruitment hours have ended.

Informed consent procedures:

Informed consent will be obtained in a two-step process. In the first step, eligible patients who agree to participate in the study will be provided with an IRB-approved informed consent information sheet. The IRB will be asked to waive written informed consent because it is a minimal risk study, and the consent form would be the only place in which the name of the participant would be recorded. The information sheet will include a description of all significant elements of the study: the assessment interview and questionnaires; risks and benefits of study procedures; alternatives to participation in the study; confidentiality; \$20 payment for participation; a statement that participation is voluntary and that the patient may withdraw at any time; and information about whom to contact with questions. The consent form will also indicate that the decision to participate will in no way influence other aspects of the patient's treatment. Patients will read the first paragraph of informed consent information sheet (or have it read to them, if they are unable) and express verbally their understanding of the key elements of the study (e.g., random assignment, the approximate duration of assessments, and risks of participation).

After completing the assessments, participants will be asked to provide informed consent (using an IRB-approved consent form with waiver of written consent) to participate in the second step of the study in which they would provide an oral fluid sample for testing amphetamines, methamphetamine (including ecstasy/MDMA), cocaine/metabolite, opiates, oxycodone, phencyclidine, THC, barbiturates, benzodiazepines, and methadone. They would be told that drug testing data will be collected without a link to their name or other identifiers and that they are free to refuse to provide the sample. They will be informed they would receive an additional \$10 for providing the sample. Participants will not be asked to provide consent for the oral fluid

test until after they have completed all other study assessments in order to avoid biasing the self-reported data.

10.2 Randomization

After providing the initial informed consent, participants will be randomly assigned to one of the two groups according to a block randomization procedure within site.

The research staff will use an Enrollment Form to document inclusion and exclusion criteria and any reasons for which an eligible participant is not randomized.

GROUP A will complete a self-administration of the two-stage instrument and then a face-toface interviewer-administration of the same instrument.

GROUP B will complete face-to-face interviewer-administration of the two-stage instrument and then a self-administration of the instrument.

10.3 Blinding

The CTN Data and Statistics Center (DSC) statistician will generate the randomization scheme for the study. The randomization procedure will be conducted through a centralized, web-based process set up by the CTN DSC. The randomization sequence will be unknown to staff until after the participant provides informed consent.

10.4 Participant Compensation

Adequate compensation for time and inconvenience for this study is appropriate and will consist of \$20 to each participant who completes the pilot test (N=30). Participants in the main study (N=2,000) will receive \$20 for completing the survey instruments and an additional \$10 for providing the oral fluid specimen.

10.5 Subject Discontinuation

All participants are allowed to withdraw consent at any stage of the study. In addition, the research assistant or PI can remove the participant from the study when there is evidence that continuing in the study might be harmful to the participant.

11.0 STUDY TIMETABLE

The study will recruit for approximately 10 months after launch, and lock the database eight weeks after the final visit.

12.0 STUDY ASSESSMENTS

The selection of assessments is based on consideration for the reported validity of the selected assessments, need for comprehensive data to select a useful set of screening and assessment items for developing a screen and the TAPS Tool, as well as costs of data collection in terms of participant time, staff time and training, and feasibility of completion in a general medical setting. Therefore, assessment questions are limited to those that have demonstrated clinical value and can contribute directly to the objectives of this study.

Each participant will respond to 4 screening items followed by the TAPS Tool which is based on the modified ASSIST-LITE.

The four screening items were based on previous reports (NIH, 2011; Smith et al., 2009; Smith et al., 2010) and modified for the present study by asking about "how often" rather than on "how many days" did the participant use substances. The five response options for the screening questions may create risk categories and are consistent with NIDA CTN's extensive work on common data elements. They are based on the response categories used in the ASSIST, but modified for easier comprehension by replacing the option "once or twice" with "less than monthly".

Each participant will complete two formats for the screen and TAPS Tool: self-administration on an iPad, and an interviewer-administration with responses entered by the RA on the iPad. The sequence of the assessment format will be randomly assigned (See Section 8.2). This will be followed by a brief survey regarding comprehension, feasibility and acceptability of the computer-administered and the interviewer-administered tool. Finally, the RA will administer the reference standard assessments.

Protocol Specific Assessments				
CRF	Done by	Screening for eligibility	A two-stage tool	Additional measures
Recruitment Form	RA	Х		
Informed consent	RA	Х		
Enrollment/Randomization*	RA			
Demographics	RA			Х
4-item screen for tobacco, alcohol, medications, illicit drugs	RA, Participant		х	
TAPS Tool	RA, Participant		х	
Survey on comprehension, feasibility, acceptability, and preference for format	RA			Х
Timeline Follow Back	RA			Х
ASSIST-Full	RA			Х

12.1 Protocol Specific Activities/Assessments

Protocol Specific Assessments				
CRF	Done by	Screening for eligibility	A two-stage tool	Additional measures
AUDIT-C	RA			Х
Modified-CIDI-SAM-2	RA			Х
Fagerström Test for Nicotine Dependence (FTND)	RA			х
The smokeless tobacco questionnaire	RA			х
Recent Prescription Medication Use	RA			х
Oral fluid testing	RA			Х
Protocol Deviation Log	RA			Х
Compensation Log	RA			Х
Study Termination	RA			Х

* Participants will be randomly assigned in counter-balanced order to receive a selfadministered two-stage instrument and a face-to-face interviewer-administered two-stage instrument.

12.1.1 Laboratory Tests

Following the interview, participants will be asked to provide an additional verbal informed consent (see above) to undergo oral fluid testing for the presence of common drugs of abuse (amphetamines, methamphetamine (including ecstasy/MDMA), cocaine/metabolite, opiates, oxycodone, phencyclidine, THC, barbiturates, benzodiazepines, and methadone). Once collected, oral fluid will be sent to an outside laboratory for analysis using methods that yield results comparable to urine drug screening (Intercept[®] immunoassay; OraSure Technologies, Bethlehem, Pennsylvania)). To aid in the interpretation of drug test results, individuals will be asked, as part of the testing procedures, if they are currently taking any drugs as prescribed by their health care provider(s) from a list of prescription opioids, benzodiazepines, and stimulants (and logged by the RA onto a CRF "Recent Prescription Medication Use"). RAs will have medication picture cards from the National Survey on Drug Use and Health as a reference in case a participant is unable to recall the name of a medication.

After completing the interview, participants will be compensated (\$20 if they complete the interview only and \$30 if they complete both the interview and the oral fluid testing) and thanked for their participation. Individuals who meet criteria for SUD of alcohol or drugs (e.g., other than tobacco) will be offered local substance use treatment referral resources, while those with current tobacco use will be given the number for their state quitline.

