6.0 STUDY DESIGN

6.1 Overview of Study Design

STUDY GROUP:

Eligible participants will be randomly assigned into one of the two groups: GROUP A and GROUP B. Both groups will first complete a demographic questionnaire (age, gender, race, ethnicity, years of education, current employment status, marital status).

GROUP A:

Will first complete a self-administered TAPS Tool on an iPad and then the same tool via a faceto-face interview (also administered on an iPad). Following tool administration, the RA will survey the participant regarding feasibility and acceptability of the interviewer-administered and self-administered versions of the tool. This will include the RA's observations regarding the amount of time it took to complete each format as well as the participant's need for assistance during the tool administration.

GROUP B:

Will first complete face-to-face interviewer-administration and then self-administration of the tool. Following tool administration, the RA will administer the survey and record observations as described above for Group A.

The RA will administer to both Groups the following reference standard assessments for substance use, sub-threshold SUD, and SUD:

- Full ASSIST for all substances.
- AUDIT-C.
- Timeline Follow Back (TLFB) interview.
- Modified CIDI-SAM 2 for all substance use diagnoses (tobacco, alcohol, and drugs).
- Fagerström Test for Nicotine Dependence (FTND).
- Smokeless tobacco questionnaire.
- Oral fluid testing for amphetamines, methamphetamine (including ecstasy/MDMA), cocaine/metabolite, opiates, oxycodone, phencyclidine, THC, barbiturates, benzodiazepines, and methadone. Oral fluid testing will be accompanied by a review of current medications to determine whether any of the drugs included in the oral fluid test are being prescribed. RAs will have medication picture cards from the National Survey on Drug Use and Health as a reference in case a participant is unable to recall the name of a medication.

Blinding:

Participants will not be blinded to study group. The interviewer will be blinded to the sequence of self-administration vs. interviewer-administration until after the patient provides informed consent.

Study Components:

Study components will include:

- An individualized pilot test of 30 adult primary care patients (across the study sites) to obtain feedback on the user-friendliness of the initial versions of the tool.

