- 7. Oral fluid samples for biological measures of objective validation: All participants will be invited to provide an oral fluid sample to test for amphetamines, methamphetamine (MDMA), cocaine/metabolite, opiates, oxycodone, phencyclidine, THC, barbiturates, benzodiazepines, and methadone. Samples can be analyzed by enzyme immunoassay (EIA). Oral fluid testing has been found to have adequate reliability compared to urine testing. (Bosker & Huestis, 2009; Cone & Huestis, 2007).

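### The prescription list used to interpret oral fluid results omits barbiturates, although they are tested and Section 6.1 promises to cover every tested drug

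*Protocol*

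**What the plan says.** Section 6.1 pairs the oral fluid test with a review of current medications. The purpose of that review is to "determine whether any of the drugs included in the oral fluid test are being prescribed", which sets no limit by class.

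Section 12.1.1 describes the same step more narrowly. The panel ends with "oxycodone, phencyclidine, THC, barbiturates, benzodiazepines, and methadone", so barbiturates are tested. The participant is then asked about drugs taken as prescribed "from a list of prescription opioids, benzodiazepines, and stimulants", and the answer goes on the Recent Prescription Medication Use form. The stated reason for asking is "To aid in the interpretation of drug test results".

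Section 8.2 includes oral fluid among the criterion measures: "Oral Fluid Testing will be the gold standards (criterion) in separate analyses for each corresponding substance", followed by the qualifier that this applies as appropriate. Section 8.1 says of the screen and the TAPS Tool that "we plan to examine the sensitivity, specificity, and ROC for each item of" each of them, against the gold standard measures.

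**The concern.** The prescription question separates two people who look the same to the assay: one who takes a drug as prescribed and one who misuses it. The tool is meant to flag only the second. For barbiturates, the list in 12.1.1 gives no means of separating them. A truthful patient with a prescription who tests positive would then look like a misuser whom the tool failed to detect, and the tool's apparent sensitivity against oral fluid would be too low.

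The timing makes this worth fixing before data are collected. Under Section 6.2 each participant is seen once, and under Section 14.3 data are anonymous with no contact information. No later coding rule can use an answer that was never requested.

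**Working it through.** The point rests on the text. The protocol has no figure of its own to reproduce.

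**Step 1: match the panel to the prescription list and to the tool (Sections 12.1.1 and 12.1.2).**

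| Panel drug | Class asked about in 12.1.1 | What the tool asks |
|---|---|---|
| Opiates, oxycodone, methadone | Opioids | Misuse only for pain relievers; any use for heroin |
| Amphetamines, methamphetamine | Stimulants | Misuse only for ADHD medication; any use for methamphetamine |
| Benzodiazepines | Benzodiazepines | Misuse only (anxiety or sleep medication) |
| Barbiturates | None | Misuse only, and not named; nearest are screen item 4 and the anxiety or sleep item |
| Cocaine, THC, phencyclidine | None | Any use (screen item 3) |

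Where the tool asks about any use, a prescription does not change the truthful answer. Where it asks only about misuse, the prescription record is needed. Barbiturates are the only panel drug that needs the record and has no class on the list.

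**Step 2: follow one patient.** The patient takes a barbiturate as prescribed. The screen and Stage II ask about medication taken for its effect, beyond the prescription or without one, so the truthful answer is no. The sample is positive. The list in 12.1.1 does not prompt for the prescription. The record then shows a negative tool and a positive assay with no explanation, exactly as it would for an undisclosed misuser.

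**Step 3: illustrate the direction. All inputs here are assumed.** Let M be the assay positives due to misuse, 0.80 the share of them the tool flags, and k the prescribed barbiturate positives that go unrecognised. Assume that none of the k is flagged and that barbiturate positives are counted with the item being assessed. Then

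apparent sensitivity = 0.80 × M / (M + k).

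| M | k = 5 | k = 10 | k = 20 |
|---|---|---|---|
| 100 (5% of 2,000) | 80/105 = 0.76 | 80/110 = 0.73 | 80/120 = 0.67 |
| 20 (1% of 2,000) | 16/25 = 0.64 | 16/30 = 0.53 | 16/40 = 0.40 |

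Here k = 5, 10 and 20 are 0.25%, 0.5% and 1% of 2,000. The result depends only on k/M, and the protocol gives neither k nor M. If k is zero, nothing changes. The table shows which way the error runs and is not an estimate.

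**The case against.** The best defence is that 6.1 governs. It promises a review of all tested drugs, the form itself is not shown, and an interviewer with picture cards may record a barbiturate that a participant mentions. That is possible. But 12.1.1 is where the procedure and form are described, and it names three classes. A mention by chance does not replace a question put to everyone.

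It is also fair to say that oral fluid is one of seven criteria, that 8.2 limits its use to where appropriate, and that Section 2.7 treats it as a measure of recent use. All of this stands and limits how far the point reaches.

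A reader might infer several stronger points that the protocol does not support:

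- **Prescribed positives count as tool misses in every class.** No section says so. For opioids, benzodiazepines and stimulants the prescription is collected, and the coding rule may be in the SAP, which is not shown.
- **The immunoassay is unconfirmed.** The protocol describes only an immunoassay but does not say that positives go without confirmation. Silence does not settle this.
- **Oral fluid is a full gold standard in both directions, so use outside its detection window becomes a tool false positive.** The qualifier in 8.2 leaves room for a narrower use. The criteria also differ in window by design: 30 days for the TLFB, 3 months for ASSIST items, 12 months for the CIDI-SAM-2.
- **The seven-substance precision claim in Section 13.2 is at risk.** That claim concerns sub-threshold and full use disorder, with precision judged against ASSIST and/or CIDI-SAM 2. Oral fluid is not named there.

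**Conclusion.** The point holds in a narrow form. Sections 6.1 and 12.1.1 contradict each other on which prescriptions are recorded, and the omitted class is one where the tool's question makes the record necessary. A prescribed barbiturate can therefore produce an uninterpretable positive in the oral fluid comparison, and the gap cannot be closed after the visit.

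The consequence is small in scope. It touches only the supportive oral fluid comparison for the sedative or prescription drug items, and only if barbiturate positives are compared with those items, a mapping the protocol does not state. The validation against the full ASSIST and the modified CIDI-SAM-2 is untouched. How much apparent sensitivity would fall cannot be computed from the document. It depends on how many participants take a prescribed barbiturate relative to the number of true misuse positives.

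**What to change.** Add barbiturates to the prescription list in Section 12.1.1 and to the Recent Prescription Medication Use form, so that the list covers every prescribable class on the panel, as 6.1 already states. The cost is one line on a form and one phrase in the protocol, with no extra test or visit. It should be done before enrolment, since earlier answers cannot be recovered.

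This point does not justify excluding participants with a current prescription from the oral fluid comparison. That would remove people who take more than was prescribed, whom the tool is meant to find. Nor does it require dropping oral fluid from 8.2. Limiting it to the share of non-prescribed positives that the tool flags would be an analysis preference, and that share would remain just as exposed to any assay false positives.
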